Escalated dosages of OCS are defined as prednisone (or equivalent OCS) 0.5 mg/kg/day for 1 to 3 weeks, followed by 0.75 mg/kg/day for ≤ 3 weeks, and 0.75 or 1.0 mg/kg/day for a final optional week.
- Transient lesions New lesions that heal within 1 week or pruritus lasting < 1 week
- Nontransient lesions New lesions that do not heal within 1 week or pruritus continuing > 1 week
- Minimal OCS therapy An oral prednisone (or equivalent OCS) dosage of ≤ 0.10 mg/kg/day
Note: For the purpose of this protocol, “oral prednisone” refers to doses/dosages of prednisone or an alternative, equivalent OCS (eg, prednisolone).
- Complete remission (CR) The absence of new lesions, complete healing of existing lesions, and absence of pruritus (except postinflammatory changes, including hypo/hyper pigmentation or skin damage)
- Partial remission (PR) The presence of only new transient lesions

- Sustained remission
 - For participants ongoing in the study when protocol amendment 2 is effective:
 - Healing of lesions with no nontransient lesions (ie, BPDAI activity score of 0) and absence of pruritus while the participant has been off both concurrent BP therapy and off efgartigimod PH20 SC for ≥ 8 weeks
 - New lesions that heal within 1 week or pruritus lasting < 1 week and clearing without treatment will not be considered to change the condition of sustained remission.
 - For participants rolling over after protocol amendment 2 is effective:
 - Healing of lesions with no nontransient lesions (ie, BPDAI activity score of 0) and absence of pruritus while the participant has been off concurrent BP therapy for ≥ 8 weeks.
 - New lesions that heal within 1 week or pruritus lasting < 1 week and clearing without treatment will not be considered to change the condition of sustained remission.
- Relapse
 - Appearance of 3 or more new lesions/month (blisters, eczematous lesions, or urticarial plaques) or at least 1 large (> 10 cm diameter) eczematous lesion or urticarial plaque that does not heal within 1 week, or extension of established lesions or daily pruritus in a participant who has achieved CDA.

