ARGX-113-2010	Final analysis	Final 1.0 of 29APR2025

Else, the participant will be considered a CR/PROff non-responder. Participants who already have the disease status CR or PR at day 1 of the treatment period or who are off OCS therapy at day 1 of the treatment period or who receive rescue therapy at day 1 of the treatment period, will be considered non-evaluable for this endpoint and will be excluded from this analysis for the corresponding treatment period.

- 3) Participants achieving CR while on minimal OCS therapy for ≥ 8 weeks (CRmin). A participant will be considered a CRmin responder if the following criteria are met simultaneously for ≥ 8 weeks (56 days):
- The participant's reported disease status is CR
 - The participant receives ≤ 0.10 mg/kg/day of prednisone (or an equivalent dose of another OCS)
 - The participant does not receive any rescue therapy (as indicated by the investigator on the eCRF). OCS used as rescue therapy will not be considered as rescue therapy if the above criterium of minimal OCS therapy is still met.

Else, the participant will be considered a CRmin non-responder. Participants who already have the disease status CR at day 1 of the treatment period or who are on minimal (≤ 0.10 mg/kg/day) OCS therapy at day 1 of the treatment period or who receive rescue therapy at day 1 of the treatment period, will be considered non-evaluable for this endpoint and will be excluded from this analysis for the corresponding treatment period.

- 4) Participants with treatment failure.

The following endpoints will be derived **for each treatment period separately and additionally for the observation phase:**

- 5) Participants achieving CR while off both OCS and efgartigimod PH20 SC for ≥ 8 weeks (CROff without IMP). A participant will be considered a responder for CROff without IMP if the following criteria are met simultaneously for ≥ 8 weeks (56 days):
- The participant's reported disease status is CR
 - The participant is off OCS therapy
 - The participant is off IMP
 - The participant does not receive any rescue therapy (as indicated by the investigator on the eCRF)

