Else, the participant will be considered a non-responder for CROff without IMP. Participants who enter the ARGX-113-2010 study under protocol version 3 (26 April 2024) or 4 (02 May 2024) will be considered non-evaluable for this endpoint. Furthermore, participants who were randomized to the placebo arm in the ARGX-113-2009 study and who enter the ARGX-113-2010 study in the observation phase, will be considered non-evaluable for this endpoint in the observation phase.

- 6) Participants achieving CR or PR while off both OCS and efgartigimod PH20 SC for ≥ 8 weeks (CR/PROff without IMP). A participant will be considered a

	Statistical Analysis Plan	
ARGX-113-2010	Final analysis	Final 1.0 of 29APR2025

responder for CR/PROff without IMP if the following criteria are met simultaneously for ≥ 8 weeks (56 days):

- The participant's reported disease status is CR or PR (continuously or alternately)
- The participant is off OCS therapy
- The participant is off IMP
- The participant does not receive any rescue therapy (as indicated by the investigator on the eCRF)

Else, the participant will be considered a non-responder for CR/PROff without IMP. A participant will be considered non-evaluable for this endpoint using the same rules as for CROff without IMP.

- 7) Duration of sustained remission will be calculated for participants achieving CR while off both OCS and efgartigimod PH20 SC for ≥ 8 weeks (i.e., responders for CROff without IMP) within a treatment period.
 - Start date of sustained remission is 1 week (7 days) after the last IMP administration in the treatment period
 - End date of sustained remission is:
 - the start date of first relapse after achieving CROff without IMP
 - the start date of a (next) treatment period
 - the start date of OCS therapy after achieving CROff without IMP
 - the start date of a rescue therapy after achieving CROff without IMP
 whichever comes first. If none of the above occurs, the participant will be censored at the end date of the study (end date of last phase).
 - Duration of sustained remission (in days) = end date - start date + 1
- 8) Relapse will be evaluated for participants having or achieving CDA, CR or PR during the treatment period (or observation phase). The evaluation period for relapse is till the end of the treatment period (or observation phase) in case a (next) treatment period starts, or else till the end of the study. Only the first relapse in a treatment period (or observation phase) will be considered.

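### Entry to the duration-of-sustained-remission analysis has no allowance for short, self-clearing lesions or itch, although the protocol's definition of sustained remission tolerates them

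*SAP*

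**What the plan says.** - **Who enters.** SAP 4.1.2 item 7: "Duration of sustained remission will be calculated for participants achieving CR while off both OCS and efgartigimod PH20 SC for ≥ 8 weeks", that is, responders for CROff without IMP within a treatment period.
- **What a responder is.** Item 5 makes a participant a responder "if the following criteria are met simultaneously for ≥ 8 weeks (56 days"). The disease criterion is "The participant's reported disease status is CR". The other criteria are being off OCS, off IMP and off rescue therapy.
- **The contrast.** Item 6 uses the same frame but accepts "The participant's reported disease status is CR or PR (continuously or alternately"). PR therefore does not count in item 5. The SAP does not use the word consecutive, but the simultaneity wording together with this contrast supports that reading.
- **How duration runs.** Item 7 starts the clock 7 days after the last IMP dose. It stops at relapse, a next treatment period, OCS or rescue, whichever is first. PR is not a stopping event.
- **The protocol.** In Definitions of Terms, sustained remission for participants ongoing at amendment 2 requires healed lesions with no nontransient lesions and no pruritus, while "off both concurrent BP therapy and off efgartigimod PH20 SC for ≥ 8 weeks". It adds that new lesions healing within 1 week, or pruritus lasting under 1 week, and "clearing without treatment will not be considered to change the condition of sustained remission". The same list counts brief pruritus as a transient lesion and defines PR as the presence of only new transient lesions.
- **No departure is logged.** SAP section 6.1 has no entry.

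**The concern.** The events that the protocol says leave sustained remission intact are the events that the disease-status scale calls PR. Item 7 has no tolerance for them before entry and full tolerance after it. Inclusion can then depend on the day on which a minor episode happens to fall.

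This matters because duration of sustained remission is a named secondary endpoint. A participant with an early PR episode has to stay relapse-free until that episode ends and a further 56 days pass, instead of 56 days in all, yet duration is still counted from 7 days after the last dose. Shorter remissions are the more likely to fail that longer requirement. The Kaplan-Meier summary would then describe a group selected for longer remissions, and fewer participants would be counted in sustained remission than the protocol definition gives.

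**Working it through.** The documents give no expected duration, relapse rate or PR rate, so there is no stated figure to reproduce beyond 8 × 7 = 56 days, which is correct.

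**1. A record that the two rules treat differently.** Count days from the last IMP dose as day 0, with no OCS or rescue: CR on days 1–40, PR on days 41–45 (one transient lesion, untreated), CR on days 46–95, relapse on day 96.
- SAP item 5: the CR runs are 40 and 95 − 46 + 1 = 50 days. Both are below 56, so this is a non-responder and is not in item 7.
- With the protocol's tolerance: days 1–95 form one run of at least 56 days, so the participant enters. By the SAP's own formula the duration is 96 − 7 + 1 = 90 days.
- Had the PR episode begun on day 70, the participant would have entered under both rules, since days 1–56 are all CR.

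**2. When one episode can exclude.** Take an off-drug window of W days, all CR except one PR episode of d days that starts after s CR days. No 56-day CR run exists only if s < 56 and W − s − d < 56. Both cannot hold once W ≥ 55 + d + 55 + 1, which is 118 days for d = 7 (the window includes the episode) and 114 for d = 3. For d = 7 there are W − 6 possible start days. The share that excludes is:

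| W (days) | Excluding / possible starts | Share |
|---|---|---|
| 56 | 50/50 | 1.00 |
| 63 | 55/57 | 0.97 |
| 70 | 48/64 | 0.75 |
| 84 | 34/78 | 0.44 |
| 98 | 20/92 | 0.22 |
| 112 | 6/106 | 0.06 |
| 118 | 0/112 | 0 |

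**3. Illustrative effect, at most one episode (all rates assumed).** Window uniform on 84–280 days; 10%, 30% or 50% of participants have one 7-day PR episode starting in the first 56 days; exponential relapse with median 120 or 200 days; hazard ratio for relapse after PR of 0.5, 1 or 2. This makes 18 scenarios.
- Lost among those with an episode who would otherwise qualify: 11% to 35%. Lost among all who would qualify: 1% to 15%.
- The median was higher under the SAP rule in all 16 scenarios where it was reached, by 2 to 23 days. It was reached under neither rule in the other 2.
- Examples with 30% having an episode and a 120-day relapse median, SAP rule versus tolerant rule: 186 vs 177 days (hazard ratio 1), 169 vs 157 (hazard ratio 2), 211 vs 205 (hazard ratio 0.5).

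**4. Illustrative effect, recurring episodes (all rates assumed).** 238 days of off-drug follow-up, 5-day episodes at 0.5, 1 or 2 per 12 weeks. About 5%, 10% and 26–27% of remissions of at least 56 days are lost with a 24-week relapse median, and about 3%, 7% and 21% with 40 weeks. At 24 weeks and 1 episode per 12 weeks, 34% of remissions of 56 to under 118 days are lost against 3% of longer ones. The 24-week median moves from about 223 to 235 days at the lowest rate. It is not reached at the higher rates, but follow-up ends only 15 days beyond 223, so that should not be read as a large shift.

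**The case against.** **The tolerance may apply only once remission exists.** On this reading, saying that a short episode "will not be considered to change the condition of sustained remission" presupposes an established condition, and the SAP complies because PR ends nothing after entry. This does not hold for entry. The condition itself is worded as no nontransient lesions, so the allowance is part of what has to be met, and transient lesions include brief pruritus. The bracketed BPDAI activity score of 0 and the absence of pruritus give the stricter reading some support, which is a further reason for the SAP to state its rule.

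**A reader might infer that anyone with one short PR episode is dropped.** The documents do not support that. Any other 56-day CR run in the same off-drug stretch still qualifies, and step 2 shows that the risk is confined to windows under 118 days. Nor does the protocol fix a duration that the SAP gets wrong: it defines a condition and gives no start date or formula.

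**The breaks may not be in the data.** SAP 4.1.1 says investigators report best status in dated episodes, and off-drug visits are every 8 weeks. A lesion that heals between visits may never be coded as PR. This stands and limits the size. It does not remove the mismatch, because investigators are asked to look for transient lesions and item 6 foresees CR and PR alternating.

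**Little depends on it.** The endpoint is secondary and descriptive. Participants who entered under protocol versions 3 or 4 are non-evaluable for item 5 and so cannot reach item 7. CR/PROff without IMP is tabulated beside CROff without IMP, and time to relapse does not use this filter. All true, but none of these gives the duration under the protocol definition. Most of the minimum on duration also comes from the protocol's own 8-week requirement, not from the CR-only rule.

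**Conclusion.** The mismatch is real and should be corrected. Item 7 applies a stricter entry condition than the protocol's definition of the endpoint it reports, is inconsistent with its own tolerance after entry, and the departure is not recorded.

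The consequence is an upward tendency in the Kaplan-Meier duration and an understated number in sustained remission. The direction was the same in every scenario where a median was reached, including those where PR halved the relapse hazard. The size cannot be found from the documents. With at most one episode the assumed inputs give 2 to 23 days on the median and 1% to 15% of qualifiers lost. Frequent recurring episodes would raise the loss to about a quarter. Sparse visits and best-status reporting would lower it. A single 7-day episode has no effect when the off-drug window is at least 118 days and otherwise all CR. A reader might take the simulated figures as an estimate of bias in this trial. They are not, because every rate in them is assumed.

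**What to change.** For item 7 only:

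1. Define a separate qualifying event: at least 56 days off IMP, OCS and rescue with status CR, where PR intervals within the protocol's 1-week tolerance that clear without treatment do not break the run. Match the protocol's boundaries (lesions healed within 1 week, pruritus under 1 week). Say how clearing without treatment is checked, including against topical corticosteroid records, which item 5 does not screen.
2. Anchor the relapse, OCS and rescue end dates to this event. They are now tied to achieving CROff without IMP, which newly admitted participants never do.
3. Leave items 5 and 6 unchanged. Item 6 is not a substitute for the entry rule, because it also admits continuous PR.
4. Report how many participants enter only through the tolerance, and list their PR intervals, since the protocol sets no limit on repeats.

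If the stricter rule is intended, record it in SAP 6.1 as a departure and report how many participants meet item 6 but not item 5.

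The cost is a short SAP change, minor programming on disease-status episodes already collected, and a possibly shorter reported median.

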Similar frequency tabulations will be created for the number and percentage of participants who achieved:

- CR/PROff
- CRmin
- Treatment failure

Similar frequency tabulations, based on the ROL analysis set, will be created for:

- CROff without IMP
- CR/PROff without IMP
- Relapse

Duration of sustained remission and time to relapse will be descriptively presented with median times, quantiles and number and percentage of censored observations and observations with event. Only the participant's first evaluation during the study will be included as observation.

Duration of sustained remission will be presented for the SAF analysis set.

A frequency tabulation will be created for categorized severity of relapse, for the participant's first relapse during the study.

	Statistical Analysis Plan	
ARGX-113-2010	Final analysis	Final 1.0 of 29APR2025

Descriptive statistics will present the actual values, changes and percent changes from study baseline of the BPDAl activity and total scores per analysis visit (baseline and last assessment).

Frequency tabulations will be provided for the outcome of IGA-BP per analysis visit (baseline and last assessment). Additionally, cumulative percentages (starting with the best outcome result) will be calculated.

Descriptive statistics will present the actual values and changes from study baseline of the itch NRS 24-hour average and worst scores per analysis visit (baseline and last assessment).

Descriptive statistics will be provided for the C-GTI scores AIS and CWS at the last assessment.

Frequency tabulations will be provided for the outcomes of the ABQOL (17 items), EQ-5D-5L (5 dimensions) and DLQI (10 items), similar to the frequency tabulations of the IGA-BP outcomes. Descriptive statistics on absolute values and changes from study baseline for EQ-5D-5L VAS score, DLQI score and Total ABQOL score will be calculated per analysis visit (baseline and last assessment), similar to the descriptive statistics of the itch NRS scores.

Listings will be created for:

- Disease status, including the derived response variables (CROff, CR/PROff, CRmin, etc.)
- Duration of sustained remission and time to relapse, including the reason for censoring (if applicable) and the severity of relapse
- Lesion assessments
- BPDAl assessments
- IGA-BP assessments
- Itch NRS assessment
- Calculated C-GTI scores and complementary GTI specific list (GTI-SL)
- ABQOL, EQ-5D-5L and DLQI data

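### SAP item 7 gives no duration of sustained remission to observation-phase responders whom item 5 counts, contrary to the heading above both items

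*SAP*

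**What the plan says.** The heading over items 5 to 10 in SAP section 4.1.2 says that these endpoints are derived "for each treatment period separately and additionally for the observation phase".

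- **Item 5** (CROff without IMP) follows that heading. Participants who entered under protocol v3.0 or v4.0 are non-evaluable throughout. Participants from the placebo arm of ARGX-113-2009 who enter in the observation phase "will be considered non-evaluable for this endpoint in the observation phase". Those from the efgartigimod arm who entered earlier stay evaluable there.
- **Item 7** (duration of sustained remission) is limited to "i.e., responders for CROff without IMP) within a treatment period". Its clock rule reads: "Start date of sustained remission is 1 week (7 days) after the last IMP administration in the treatment period". The end is the earliest of relapse, OCS start, rescue start or "the start date of a (next) treatment period", with censoring at the end of the last phase.
- **Items 8 and 9** (relapse and time to relapse) name the observation phase explicitly.

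SAP section 4.1.3 sets the populations. For the item 5 proportion: "Similar frequency tabulations, based on the ROL analysis set, will be created for" CROff without IMP (Table 14.2.1.4). For item 7: "Duration of sustained remission will be presented for the SAF analysis set" (Table 14.2.1.6). Under SAP section 2.1.1, SAF requires at least one IMP dose.

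The protocol (Definitions of Terms) describes sustained remission, for participants ongoing when amendment 2 takes effect, as healed lesions and no pruritus "while the participant has been off both concurrent BP therapy and off efgartigimod PH20 SC for ≥ 8 weeks". It does not require a dose in this study.

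**The concern.** Item 7 is the only one of items 5 to 10 whose wording excludes the observation phase. An observation-phase responder has no treatment period at that point and no last dose from which to start the clock, so no duration can be computed even if the heading is taken to apply.

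Duration of sustained remission is a named secondary endpoint in protocol section 3, under an objective about durability of response. Participants who enter this study off drug and stay in complete remission off OCS and rescue are directly relevant to it, and the plan already counts them as responders. A reader would expect the duration table to describe the responders in the proportion table. As written it describes a subset, and SAP section 6.1 records no reason.

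**Working it through.** The plan states no figure to reproduce. The check has three parts.

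**1. Following one participant through the rules.** Take a participant from the efgartigimod arm of ARGX-113-2009 who entered before v3.0, was not dosed at the baseline visit, and was in complete remission off OCS and rescue for at least 56 days in the observation phase.

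| Step | Rule | Result |
|---|---|---|
| First phase | SAP 2.2.1, Table 2: not dosed at baseline | Observation phase |
| Evaluable for item 5 in that phase? | Not a v3.0/v4.0 entrant, not from the placebo arm | Yes |
| Item 5 result | All criteria met for 56 days | Responder, Table 14.2.1.4 (ROL) |
| Item 7 population | Response within a treatment period | Not met |
| Item 7 start date | Last IMP in the treatment period + 7 days | Does not exist |
| Table 14.2.1.6 set | SAF, if never dosed | Not in the set |

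If the participant is dosed later, the last row changes, because the participant joins SAF. The two rows above it do not change for the observation-phase remission, which is still lost. Such a participant can enter Table 14.2.1.6 only with a later treatment-period remission. Changing SAF to ROL alone would therefore not repair the table.

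**2. Greatest duration that can be recorded.** Inputs: study length of about 56 weeks (protocol section 4.1), baseline as day 1, visit windows ignored. The nominal last day is 7 × 56 + 1 = 393. Item 7 defines duration as end − start + 1. With the last dose at week w, the start day is (7w + 1) + 7, so the maximum is 393 − (7w + 8) + 1 = 386 − 7w.

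| Last IMP dose | Maximum duration (days) |
|---|---|
| Week 0 | 386 |
| Week 8 | 386 − 56 = 330 |
| Week 16 | 386 − 112 = 274 |
| Week 24 | 386 − 168 = 218 |
| None in this study, clock from day 1 (assumed) | 393 − 1 + 1 = 393 |

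These are ceilings on follow-up. They are not observed durations.

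**3. How far the median could move.** The documents give no counts or durations, so every input here is assumed. There are 15 treatment-period responders with true median 20 weeks and follow-up uniform on 12 to 36 weeks, and 5 or 10 observation-phase responders followed to week 56. Each duration is 8 weeks plus an exponential residual. Results are medians, over 3000 simulated data sets, of the Kaplan-Meier median. A median not reached counts as above all observed values.

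| Observation-phase responders | Their true median (weeks) | Median as planned (weeks) | Median with all responders (weeks) |
|---|---|---|---|
| 10 | 14 | about 20 | about 17 |
| 10 | 20 | about 20 | about 20 |
| 5 | 40 | about 20 | about 23 |
| 10 | 40 | about 20 | about 27 |
| 10 | 60 | about 20 | about 31 |

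The sign and size of the shift follow from the assumed median of the omitted group.

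**The case against.** **The restriction may be deliberate.** Population, clock and analysis set in item 7 agree with one another, and protocol section 4.2 speaks of sustained remission after stopping efgartigimod. Measuring from a dose given in this study is a defensible choice. But the heading then claims too much, the reason is unstated, and the protocol definition has no such limit.

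**A reader might infer that these participants have no duration anywhere.** The documents do not support that. Item 9 covers the observation phase, and Table 14.2.1.8 gives time to relapse on ROL. For someone in remission from rollover with no OCS or rescue, it is close to the missing quantity. It is not a substitute in general: it starts at the first day with CDA, CR or PR and does not end at the start of OCS or rescue.

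**A reader might infer that the longest remissions are left out.** Only possible follow-up is longer, and the margin can be as small as 393 − 386 = 7 days. IMP could also be started at the investigator's discretion after amendment 2 (protocol section 6.3.2, situation 3A), and that would end the duration under item 7.

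**A reader might infer downward bias.** Item 7 restricts by phase, so it drops short observation-phase remissions that ended in relapse and dosing as well as long ones. A downward bias is possible but not established.

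**The affected group may be small**, and the endpoint is descriptive with no hypothesis test. Both points stand. They limit the weight of the finding but do not remove the conflict.

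**Conclusion.** The conflict is real. Item 7 disagrees with its heading and with item 5, and the number of observations in Table 14.2.1.6 need not match the responders in Table 14.2.1.4. The omission affects participants from the efgartigimod arm of ARGX-113-2009 who entered before v3.0 and met CROff without IMP in the observation phase, including those dosed later.

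The documents do not allow the effect on the estimate to be sized. In the assumed example, the median for all responders ranges from about 17 to about 31 weeks against about 20 as planned, with no material shift when durations are equal. What can be concluded is that the reported duration describes only some of the counted responders. That is worth correcting for a named secondary endpoint, but it does not affect the primary safety analysis.

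**What to change.** - **Population.** In item 7, extend the responder condition to a response in a treatment period or in the observation phase.
- **Clock.** For observation-phase responders, start on the first day of the qualifying 56-day run in ARGX-113-2010. Keep item 7's existing end and censoring rules.
- **Table.** Base Table 14.2.1.6 on ROL participants evaluable for item 5, and amend section 4.1.3 to match.
- **Presentation.** Show treatment-period and observation-phase responders in separate rows. Footnote the different time origins, and note that remissions begun before rollover are counted only from rollover. Treat any pooled total as supplementary, because it mixes two definitions of duration. State how the rule of using only a participant's first evaluation works across the two rows.

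The cost is a wording change in sections 4.1.2 and 4.1.3 and one reprogrammed table, with no new data collection. If the sponsor intends the restriction, the minimum is to narrow the heading for item 7, give the reason, and footnote why the counts in the two tables differ.
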